The control participants will all participate in baseline and endpoint surveys with the CHWs. They will also complete a Session 1 educational session. Control participants will not be contacted during the rest of

the 6-month intervention phase and will be contacted by the clinic staff only when the intervention is complete among treatment participants. Those in the first wave will be offered the intervention in the second wave. The second wave control group will be offered educational sessions as a point of service and not as part of research (i.e., wait-listed control study design).

B1. Data Analysis and Monitoring

The NYU site will lead the data analysis portion of the study, with input and feedback from Emory research staff.

Specific Aim 2 Analysis.

Specific Aim 2: To compare the effect of the intervention with usual care on achieving BP control among individuals with diabetes. The primary outcome will be the proportion of eligible patients at a practice site to achieve BP control (130/80 mmHg) six months following the index office visit. *Hypothesis:*

Individuals receiving care during the implementation of the intervention will be more likely achieve BP control six months following the index office visit than individuals receiving care as usual. The primary outcome of interest is the proportion of patients who achieve BP control. The secondary outcomes of interest include changes in HbA1c, SBP and DBP, and BMI at 6 months. For analyses of both primary and secondary outcomes, a logistic regression model will be used to estimate the CHW effect on outcomes (see equation 1):

$$(1) \quad \text{logodds}[P(Y_{ij})] = \beta_0 + \gamma_j + \beta_1 H$$

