Using the primary outcome, HTN control, as an example, Y_{ijk} indicates state of HTN control at the end of the 6 months for patient i , in clinic site j . $Y_{ijk}=1$ if patient achieved HTN control, $Y_{ijk}=0$ if otherwise. $H_i=1$ if patient i was randomized to the CHW intervention, $H_i=0$ if otherwise (i.e., control group). γ_j is a fixed effect for clinic site. $\mu + b_j$ is the log odds of HTN control for patients randomized to the control group in the first 6 months. β_1 represents the log odds ratio of HTN control for those randomized to the CHW intervention compared to those randomized to the control group. A test will be conducted with the following null and alternative hypotheses: $H_0 : \beta_1 = 0$ vs. $H_A : \beta_1 \neq 0$ to assess whether or not the CHW intervention had an effect on HTN control after 6 months. We will conduct exploratory, secondary subgroup analyses to see which subgroups may achieve greater benefit from the intervention. In addition, we will assess an alternative measure of HTN control, using an ADA BP control definition of 140/90 mmHg to evaluate the effect of the CHW intervention. And finally, we will compare the findings from this Atlanta-based study with our ongoing trials in the NYC area. The datasets from each respective study will not be combined; they will be analyzed separately. Sex as a biological variable will be addressed by exploring gender as a potential moderator of intervention effects.

Specific Aim 3: Analysis

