We will conduct cross-sectional analyses, using EHR-based samples South Asians aged 18+ years living in the greater Atlanta and New York City areas from two large healthcare systems. Prevalence values and 95% CIs will be estimated by study site, sex, age-group, and BMI category. Participant characteristics will be stratified by sex and compared by study using χ^2 test or ANOVA as appropriate. The non-normally distributed variables of fasting and 2-h plasma glucose will be log transformed. The effect of location of residence (Atlanta or New York) on the risk of diabetes and prediabetes will be assessed using standardized polytomous regression. Initially, an unadjusted regression model will be created to compare the individual association between study location and prevalence of diabetes and prediabetes. Subsequent multivariable models were then created to adjust for covariates including age, sex, blood pressure, BMI, and educational status. All analyses will be performed using SAS, version 9.4 (SAS Institute, Cary, NC).

B2. Power Calculation.

We conservatively estimate a 20% difference in effect size (i.e., BP control) when comparing intervention and control group participants. Our power calculation was based on our previous studies. Based on results from these studies, at six-month follow-up we conservatively assume a 15% BP control rate for the control group and 35% BP control rate for the treatment group. In our previous work, BP control rates at baseline varied; however, in the proposed study all participants will have uncontrolled BP at baseline. Further, in our past work control group participants experienced almost no change in BP control at follow-up; here we conservatively estimate a 15% BP control rate at follow-up. Accrual of 162 participants, evenly randomized to intervention or control groups, will provide greater than 80% power to detect this difference, using a 2-sided, 0.05-level test (i.e., approximately 81 intervention and 81 control participants). These calculations assume a 10% loss to follow-up.

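### A logistic model is prescribed for all secondary outcomes, but changes in HbA1c, SBP, DBP and BMI are continuous and no cut-offs are defined

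*Combined protocol and SAP*

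**What the plan says.** Study Outcomes (section II, Phase 2) and the Specific Aim 2 analysis (section VII.B1) list the secondary outcomes in the same words: "The secondary outcomes of interest include changes in HbA1c, SBP and DBP, and BMI at 6 months". VII.B1 then gives one model for everything: "For analyses of both primary and secondary outcomes, a logistic regression model will be used to estimate the CHW effect on outcomes". Equation (1) sets the log odds of the outcome equal to an intercept, a clinic-site effect and a treatment term.

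The explanation below the equation is introduced with "Using the primary outcome, HTN control, as an example", so the model is meant to reach beyond BP control. It says that Y "indicates state of HTN control at the end of the 6 months for patient" and codes it 1 or 0. The treatment coefficient "represents the log odds ratio of HTN control for those randomized to the CHW intervention compared to those randomized to the control group".

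The same section adds one further binary measure: "we will assess an alternative measure of HTN control, using an ADA BP control definition of 140/90 mmHg".

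**The concern.** A logistic model needs an outcome that is 0 or 1. A change in HbA1c, blood pressure or BMI is a number on a continuous scale. An analyst following the plan has two options: depart from it, or turn each change into a responder status using a cut-off that the plan does not supply.

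Three things are at stake:

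- **Prespecification.** For all four named secondary outcomes, the model or the cut-point would be chosen later, possibly with the data in view.
- **Interpretation.** The result would be an odds ratio for crossing a threshold, not the mean difference that an outcome defined as a change calls for.
- **Precision.** Dichotomising discards information. Equation (1) also has no baseline value, so a linear analysis built on the same terms would forgo a gain in precision and leave any chance baseline imbalance in the change.

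**Working it through.** **1. Does the text allow another reading?**

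| Possible reading | What the document shows |
|---|---|
| Responder outcomes were intended | No section gives a cut-off for a change in HbA1c, SBP, DBP or BMI |
| The secondary outcome meant is BP control at 140/90 | VII.B1 adds it separately, as an alternative measure of HTN control; it is not among the listed secondary outcomes |
| An ordinal logistic model was intended | Equation (1) has a single intercept and Y is 0/1 |
| The logistic model is for the primary outcome only | The sentence names both kinds of outcome, and HTN control is only the example |
| A suitable model is given elsewhere | The ANOVA, chi-square and log-transformation text (IV.A2, and the first Specific Aim 3 analysis in VII) concerns the cross-sectional EHR study |

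None of these rescues the text. As a direct check, a binary logit was fitted to a simulated continuous change score for 146 participants. It stopped with an error because the outcome was not between 0 and 1.

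**2. The plan's own figure.** The only sample-size calculation is in VII.B2. It concerns the binary primary outcome: "we conservatively assume a 15% BP control rate for the control group and 35% BP control rate for the treatment group". The test is two-sided at 0.05, with 10% loss. The pooled two-proportion formula is

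n per arm = [1.960·√(2·0.25·0.75) + 0.842·√(0.15·0.85 + 0.35·0.65)]² / 0.20² = 72.4, rounded up to 73.

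That is 146 evaluable, and 146/0.9 = 162.2, which agrees with the stated 162. Power with 73 evaluable per arm is 80.3%. The figure reproduces and is not in dispute. The document states no power for any secondary outcome.

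**3. Information lost by dichotomising.** For a normal outcome split at proportion p, efficiency relative to comparing means is φ(z_p)² / [p(1−p)]:

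- p = 0.50: 0.637
- p = 0.35: 0.603
- p = 0.20: 0.490
- p = 0.15: 0.426

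The document gives no SD or effect size for these outcomes, so power can only be illustrated. Assume normal change scores with equal SD and a standardised effect d. Take 73 evaluable per arm (81 × 0.9) or 293 (326 × 0.9, from the enrolment target in V.A). The cut is placed where 50% or 20% of controls respond.

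| Evaluable per arm | d | Power, means | Power, 50% cut | Power, 20% cut |
|---|---|---|---|---|
| 73 | 0.2 | 23% | 16% | 14% |
| 73 | 0.3 | 44% | 30% | 26% |
| 73 | 0.4 | 68% | 48% | 43% |
| 73 | 0.5 | 86% | 66% | 61% |
| 293 | 0.2 | 68% | 49% | 41% |
| 293 | 0.3 | 95% | 82% | 75% |

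**4. Baseline value.** Let r be the baseline-to-follow-up correlation, with equal variances at the two times. In units of the outcome variance, the raw change has variance 2(1−r). The 6-month value adjusted for baseline has residual variance 1−r² = (1−r)(1+r). The ratio is (1+r)/2, so the reduction is (1−r)/2. For assumed r = 0.4, 0.5 and 0.6 this is 30%, 25% and 20%. At r = 0.9 it is only 5%.

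**The case against.** The best counter-argument is that this is loose drafting with limited reach. The primary outcome is binary, equation (1) suits it, and all stated power rests on it. The error exposes itself, because software refuses to fit the model, so no wrong result would appear unnoticed. The team's earlier work, described in I.A7, reports mean SBP and DBP alongside a control rate, which suggests a comparison of means was intended. The notation points the same way: the symbols in equation (1) and in its explanation do not match.

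The size figures can also be challenged. The efficiency losses arise only if someone dichotomises, which the plan does not propose in words. The 35% and 15% splits echo the assumed BP-control rates and are not thresholds for any secondary outcome. The variance reduction compares two linear analyses, neither of which is in the plan. It also needs equal variances, which is doubtful for SBP and DBP because eligibility selects on raised BP.

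Much of this stands as a limit on size. The figures are conditional, and baseline adjustment is a gain in precision, not a correction of bias: under randomisation the unadjusted change comparison is unbiased on average. The main point is untouched. Probable intent is not a prespecified analysis, and the stated rule is inapplicable to every named secondary outcome.

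**Conclusion.** The concern holds and should be corrected before analysis. The plan explicitly assigns a model for a 0/1 outcome to four continuous outcomes and supplies neither cut-offs nor an alternative. This is a wrong instruction, not merely missing detail.

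If the outcomes were dichotomised to make the model run, at most 64% of the information would be kept under normality, and less for uneven splits. The variance gain from baseline adjustment depends on the assumed correlation and on equal variances at the two times. The conclusion that the model does not fit these outcomes depends on neither set of assumptions.

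The defect is confined to the secondary outcomes. The logistic analysis of BP control and the figure of 162 are not affected by it.

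**What to change.** In VII.B1, limit equation (1) to the two binary outcomes: BP control at 130/80 and at 140/90. For each of HbA1c, SBP, DBP and BMI, prespecify

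6-month value = b0 + b1·H + site + age stratum + gender + baseline value of that outcome,

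and report b1 as the adjusted mean difference with its 95% CI.

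Age and gender are the randomisation strata in VII.A, and III.B1 describes randomisation within site. III.B1 also allows community recruitment, so the text should say which site level those participants take. If responder analyses are wanted as well, state the cut-offs in advance and label the analyses supportive.

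The cost is one paragraph of analysis text. No new data are needed, because computing a change already requires the baseline value.

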A7. CHWs demonstrate efficacy in improving HTN and diabetes related outcomes in South Asians. Our work has demonstrated culturally adapted CHW-led interventions in community and clinical settings are acceptable and efficacious in improving HbA1c control, weight loss, self-efficacy and social support, and health behaviors for South Asian patients with diabetes, and improved BP control and medication adherence among Filipino and South Asian individuals with HTN.^{12,13,61-63} A substantial proportion of South Asian individuals in our HTN and diabetes management intervention^{13,64} (total n=640) had co-morbid diabetes and hypertension (56%, n=358), and among this subgroup, 75% had uncontrolled HTN at baseline. A combined analysis across to randomized control trial studies examining the impact of CHW-led coaching for individuals with comorbidities found that individuals in the treatment group were more likely to achieve BP control (using the ADA defined 140/90 mmHg) at study follow-up, compared to individuals in the control group (72% vs 57%, p<0.012). Mean SBP decreased from 136.2 to 129.9 (p<0.001) and mean DBP decreased from 82.8 to 78.5 (p<0.001) in the treatment group, while the control experienced a small, non-significant change in DBP and no change in SBP. The differences between groups were statistically significant (p<.05).⁶⁵ *Our study findings offer a promising model to address HTN control among South Asian individuals with diabetes that can be replicated to address disparities among South Asians living in the Southeast.*

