The proposed project takes place in two parts: part one builds upon the evidence base of the effectiveness of culturally tailored CHW interventions and proposes to replicate and scale a CHW intervention. A critical need exists to tailor, translate, and disseminate evidence-based CHW interventions to maximize impact in ameliorating co-morbid CVD disparities. Part two describes the variation of cardiovascular disease risk across South Asian populations in the US derived from electronic health records. Our study takes a first step towards filling this gap in the literature, by characterizing the burden of disease among two South Asian communities. This project will facilitate bidirectional collaboration by building this data set across two sites in the United States. This will complement ongoing work by the investigative team to replicate an efficacious intervention program delivered in NYC in Atlanta.

B. Study aims

Specific Aim 1: Provide research training, technical assistance, and capacity-building to community and clinical sites in Georgia for implementation of culturally tailored, evidenced-based CHW programs to improve HTN and diabetes management for South Asians.

Specific Aim 2: Use a multi-theoretical framework to test the effectiveness of a CHW-led intervention compared to usual care among South Asian individuals with diabetes and uncontrolled HTN in Atlanta.

Specific Aim 3: Apply RE-AIM and CFIR frameworks to delineate factors influencing reach, appropriateness, fidelity, adoption, and maintenance of the intervention within clinical and community settings to optimize intervention replication.

Sub-Aim3a: Serve as a national information and dissemination resource in the adaptation of evidence-based strategies to reduce geographic disparities in HTN and diabetes across Asian American groups.

B. Study Outcomes

Phase 1: See below: this is the planning and technical assistant phase of the proposal.

Phase 2: The primary outcome of interest is proportion of patients that achieve BP control, defined as less than or equal to 130/80 mmHg, at 6 months. The secondary outcomes of interest include changes in HbA1c, SBP and DBP, and BMI at 6 months.

Phase 3: The outcomes for the provider surveys, informant surveys, and EHR will be descriptive data to inform with to facilitate the development of intervention strategies within the larger healthcare system

III. STUDY DESIGN

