Type 2 Diabetes Mellitus	E11.00, E11.01, E11.21, E11.22, E11.29, E11.311, E11.319, E11.321, E11.329, E11.331, E11.339, E11.341, E11.349, E11.351, E11.359, E11.36, E11.39, E11.40-E11.44, E11.49, E11.51, E11.52, E11.59, E11.610, E11.618, E11.620-E11.622, E11.628, E11.630, E11.638, E11.641, E11.649, E11.65, E11.69, E11.8, E11.9, E13.00,	Therapeutic class of Antihyperglycemic, excluding medication names of Metformin and Acarbose	A1C: 4548-4, 7426-0, 4549-2, 17856-6, 59261-8, 71875-9, 62388-4, 4637-5, 55454-3, 41995-2, 17855-8

	E13.01, E13.10, E13.11, E13.21, E13.22, E13.29, E13.311, E13.319, E13.321, E13.329, E13.331, E13.339, E13.341, E13.349, E13.351, E13.359, E13.36, E13.39, E13.40-E13.44, E13.49, E13.51, E13.52, E13.59, E13.610, E13.618, E13.620, E13.621, E13.622, E13.628, E13.630, E13.638, E13.641, E13.649, E13.65, E13.69, E13.8, E13.9		
--	---	--	--

V. STUDY ENROLLMENT

A. Characteristics of the research population

The overall number of subjects expected to participate in this study is 737. This includes a total enrollment of 652 participants in the CHW Intervention (326 treatment participants and 326 control participants, accounting for 10% attrition), 10 subjects who participate in the provider surveys, 25 participants in the key informant interviews and 50 focus group participants.

CHW Intervention

Inclusion Criteria: Participants will be eligible for study participation if they meet the following criteria: a) are of South Asian ethnicity (identified through a race and language code in the EHR or at screening); b) are at least 21 years of age and younger than age 85, c); d) a diagnosis of diabetes in the EHR or self-reported through community recruitment and e) a diagnosis of hypertension or self-reported diagnosis through community recruitment; f) an uncontrolled BP reading(>130/80mmHg) in the last 6 months or at screening.

Exclusion Criteria: a) Patients under the age of 21 and older than 85 will be excluded. b) Women who are pregnant at the time of screening. c) Type 1 diabetes or diabetes secondary to other conditions (e.g. steroid-induced, pancreatic insufficiency, or chemotherapy-induced), d) inability to perform unsupervised physical activity.

No children will be enrolled in this study.

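### The alternative 140/90 control measure is looser than the >130/80 entry rule, so some participants meet it at baseline; this dilutes the contrast unless baseline status is in the model

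*Combined protocol and SAP*

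**What the plan says.** - **Entry** (section V.A, CHW Intervention inclusion criteria): "an uncontrolled BP reading(>130/80mmHg) in the last 6 months or at screening". Whether this means systolic or diastolic above the cut-off, or both, is not stated.
- **Primary outcome** (section II, Study Outcomes): control is "defined as less than or equal to 130/80 mmHg, at 6 months". Entry and primary endpoint therefore use the same cut-off.
- **Alternative measure** (section VII.B1, Specific Aim 2 Analysis): "we will assess an alternative measure of HTN control, using an ADA BP control definition of 140/90 mmHg". No restriction by baseline status is given, and the text does not say how a reading exactly at the cut-off is scored.
- **Scoring and model** (section VII.B1): the outcome "indicates state of HTN control at the end of the 6 months for patient i". Equation (1) has an intercept, a fixed effect for clinic site and a term for arm. It has no baseline blood pressure term.
- **Baseline premise** (section VII.B2, Power Calculation): "in the proposed study all participants will have uncontrolled BP at baseline". This follows from the entry rule at 130/80; nothing makes it true at 140/90.
- **Prior work** (section I, A7): "Mean SBP decreased from 136.2 to 129.9 (p<0.001) and mean DBP decreased from 82.8 to 78.5 (p<0.001) in the treatment group". No SD is given.

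**The concern.** A participant enrolled at, say, 134/84 satisfies the entry rule and is already within 140/90. This comes from the gap between the two thresholds. It does not depend on the qualifying reading being up to six months old, and would occur if every baseline reading were above 130/80.

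For such participants the 140/90 measure records whether they stay controlled. For the others it records whether they become controlled. Pooling the two without a baseline term raises the rate in both arms and shrinks the difference between them. It also makes the result depend on the baseline mix, which the plan does not report. That mix matters for interpretation: the prior combined analysis in section I, A7 used 140/90, and section VII.B1 plans a comparison with the New York trials. Without baseline 140/90 status, a reader cannot tell a different effect from a different case mix.

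**Working it through.** **1. The plan's own figure.** The documents give no power and no baseline share for 140/90. The stated sample size is for the 130/80 endpoint: "we conservatively assume a 15% BP control rate for the control group and 35% BP control rate for the treatment group", with 162 participants, a two-sided 0.05 test and 10% loss. The usual two-proportion formula gives 73 evaluable per arm. Since 81 × 0.9 = 72.9, power is 80.3%, so the stated figure reproduces. Elsewhere the protocol plans 326 per arm; 326 × 0.9 = 293 evaluable. Both sizes are carried below because the documents do not reconcile them.

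**2. Share already below 140/90 at entry.** Input from the documents: mean 136.2/82.8. Assumed: bivariate normal, correlation 0.5, SDs as shown. Simulated values are kept only if they satisfy entry, and the share with SBP <140 and DBP <90 is counted.

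| Assumed SD (SBP/DBP) | Entry = systolic or diastolic | Entry = both |
|---|---|---|
| 13/9 | 44% | 27% |
| 15/10 | 40% | 23% |
| 18/11 | 36% | 18% |

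If the mean were instead 145/86 (assumption), the share is 12-25% across both readings. With SDs from 12/8 to 20/12, correlations from 0.4 to 0.7 and either handling of a reading exactly at the cut-off, the ranges at 136.2/82.8 widen to 30-49% and 13-33%.

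**3. Rough cross-check from prior rates.** Section I, A7 reports 75% uncontrolled at baseline and 57% of controls within 140/90 at follow-up. Section VII.B2 says control-group control hardly changed. If the 75% is at 130/80, and the 57% approximates the baseline rate, the share is (57 − 25)/75 = 43%. The threshold behind the 75% is not stated, so this is only supportive.

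**4. Dilution.** Overall rate = (1 − s) × rate in those not yet controlled + s × rate in those already controlled, where s is the share already controlled. All response rates here are illustrative.

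- *Illustration A*, s = 0.40, 45% vs 25% in the first group and 85% vs 80% in the second:
  - Treatment: 0.6 × 45 + 0.4 × 85 = 61%.
  - Control: 0.6 × 25 + 0.4 × 80 = 47%.
  - The difference is 14 points instead of 20, and the odds ratio is 1.76 instead of 2.45.
- *Illustration B*, s = 0.40, 35% vs 15% in the first group and 90% in both arms of the second:
  - Treatment: 0.6 × 35 + 0.4 × 90 = 57%.
  - Control: 0.6 × 15 + 0.4 × 90 = 45%.
  - The difference is 12 points.
- *Illustration B with s = 0.20*, nearer the both-required reading: 46% vs 30%, a difference of 16 points.

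**5. What a baseline term recovers.** Simulated power at s = 0.40, range over illustrations A and B:

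| Evaluable per arm | Arm only | Arm + baseline 140/90 status |
|---|---|---|
| 73 | about 34-40% | about 46-48% |
| 293 | about 83-94% | about 97% |

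**The case against.** The case against runs as follows.

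- **The full-sample measure is legitimate.** The outcome is a state at six months, compared between randomised arms. Remaining below 140/90 can itself be a benefit, and a full-sample rate is the natural comparator for the earlier 72% vs 57%. This stands. A reader might infer that those already below 140/90 cannot succeed, or that the comparison is biased. Neither follows: they score as successes by staying controlled and as failures by rising above the cut-off, in both arms alike.
- **The plan does not mislabel the measure.** A reader might take the word achieved in section VII.B1 as describing the 140/90 outcome. It belongs to the worked example, which is the primary outcome. The 140/90 sentence speaks only of an alternative measure of control. This stands; the suggested label is a clarification.
- **The stakes are limited.** This is one alternative measure with no stated power, multiplicity role or decision rule, and changes in SBP and DBP are already secondary outcomes. This stands. The documents do not call 140/90 a robustness check, so a claim that a weak result would undercut the primary finding is speculation.
- **The size rests on assumptions.** No SD or correlation is given, and the entry wording allows two readings. This stands, which is why both ranges are shown. It does not remove the mismatch, only the certainty about its size.
- **Restricting the analysis changes the question.** Selecting on a high baseline reading reduces the sample, and regression to the mean raises the control rate in both arms. This stands against making the subset the definition. It is no argument against adjusting the full-sample analysis.

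**Conclusion.** The thresholds do not match, and the plan has no provision for it. Some participants will meet 140/90 at baseline under a perfectly enforced entry rule. At the prior-work mean the share is about 36-44% if either component qualifies and 18-27% if both must, on assumed SDs of 13/9 to 18/11 and correlation 0.5; it is lower if this trial's baseline pressures are higher. The consequence is a higher rate in both arms and a diluted contrast, by 6 to 8 of 20 points in the 40% illustrations. It also costs power that a baseline term would partly recover. A reader might go further and conclude that the primary result is compromised. The documents do not support that, because the primary endpoint and entry share the 130/80 cut-off.

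**What to change.** In section VII.B1:

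- Keep the 140/90 analysis in all randomised participants and describe it as *BP control at 140/90 at 6 months*.
- Add baseline 140/90 status, or baseline SBP and DBP, to equation (1) for this outcome. Specify that it is measured before randomisation. Section III.B2 puts the baseline survey straight after consent, the Documentation of Consent section allows two weeks, and section VII.A places randomisation after Session 1 without fixing the order relative to the survey.
- Tabulate baseline 140/90 status by arm.
- As a supporting subgroup analysis, report control at 6 months among those at or above 140/90 at baseline, noting the smaller sample and that regression to the mean raises the rate in both arms.
- Use the same inequality at the cut-off in both versions, and state whether entry requires either or both components above 130/80.

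The cost is a few sentences and one table row; blood pressure is already part of the survey measures. The adjusted odds ratio is conditional on baseline status, so the crude proportions by arm should be shown beside it for comparison with the earlier results.

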After letters from the provider practices of the 3 participating clinical sites have been mailed to eligible patients or they have been notified of the study by their provider, CHWs will contact patients via mailing and phone calls to invite them to enroll into the intervention. CHWs will call patients a maximum of ten times over a two-week period at varying times of day to invite them to enroll into the study. In addition, list of eligible treatment participants will be shared with primary care physicians who will be encouraged to refer patients to contact CHWs during routine visits. CHWs will also table at primary care provider (PCP) clinics and community events to enhance recruitment and enrollment. During the recruitment call, CHWs will conduct a brief screening to confirm eligibility (see Screening Form). If eligible, patients will be invited to complete an in-person consent form (See Consent Brochure and Consent Signature Page for CHW Intervention) and survey (see Participant Survey) that assesses baseline demographic and logistical information, such as preferred language and session availability. Participants must sign a consent form in order to participate, which will be administered by the CHW or bilingual study coordinator.

Surveys will be collected from all participants at baseline and 6 months. Baseline surveys will be conducted by a CHW or bilingual study coordinator immediately following consent. Six-month surveys will be conducted in person by a study staff within two weeks of completion of the CHW coaching component of the intervention. Survey measures will be developed based on their 1) brevity; 2) presence of domains with face validity for Asian American or low literacy communities; and 3) valid psychometric properties, thus enhancing scientific rigor. Survey measures include weight and blood pressure measurements, as well as questions about self-efficacy, medication adherence, and referrals to social services.

Patient-engagement measures: Contact with eligible treatment group participants will be collected in REDCap or on paper-based CRFs, including phone contact attempts, patients' intervention status (declined, enrolled, not reached etc.), completion of intervention activities (such as health education sessions and phone-based health coaching), and completion of data collection, referrals, and intervention activities across sites and CHWs.

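### The power statement assumes everyone is uncontrolled at baseline, but the entry rule lets in people who may already be at or below 130/80, and the primary model ignores baseline BP

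*Combined protocol and SAP*

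**What the plan says.** - **Premise of the power calculation (VII.B2).** Baseline control varied in the team's earlier studies, but "in the proposed study all participants will have uncontrolled BP at baseline". For the control arm, "here we conservatively estimate a 15% BP control rate at follow-up"; the treatment arm is set at 35%. On that basis 162 participants (81 per arm, 10% loss, two-sided 0.05) are said to give more than 80% power.
- **Entry rule (V.A, criterion f).** The BP requirement is "an uncontrolled BP reading(>130/80mmHg) in the last 6 months or at screening".
- **How eligibility is checked (III.B2).** "During the recruitment call, CHWs will conduct a brief screening to confirm eligibility".
- **Baseline BP (III.B2).** It is taken with the survey: "Survey measures include weight and blood pressure measurements". Nothing makes entry depend on that reading.
- **Endpoint (II, Study Outcomes).** The primary outcome is the "proportion of patients that achieve BP control, defined as less than or equal to 130/80 mmHg, at 6 months". In VII.B1 the response variable "indicates state of HTN control at the end of the 6 months".
- **Model (VII.B1, equation 1).** Logistic regression with a fixed effect for clinic site and a term for arm. There is no baseline BP term.
- **Alternative measure (VII.B1).** The analysis will be repeated "using an ADA BP control definition of 140/90 mmHg".

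**The concern.** The two sections describe different populations. B2 describes a cohort in which nobody is controlled at the start, so that every controlled participant at six months has changed state. Criterion (f) describes a cohort with at least one high reading at some point in six months. A single past high reading can be followed by treatment, ordinary variation or regression to the mean, so a qualifying participant may be at or below 130/80 at the baseline survey.

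Three things follow if that happens. The 15% and 35% rates, set for an all-uncontrolled cohort, may not describe the mixed cohort, and the difference between arms may be diluted. The outcome counts remaining controlled together with becoming controlled, although the plan speaks of achieving control. And a strong predictor of the outcome, already measured, is left out of the model.

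The 140/90 measure has the same feature without any assumption about variation over time. Someone whose qualifying reading is 131-139 systolic and 81-89 diastolic satisfies criterion (f) and already meets 140/90 on that same reading.

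**Working it through.** **1. Reproduce the stated figure.** Inputs from VII.B2: p0 = 0.15, p1 = 0.35, two-sided alpha 0.05, 80% power, 10% loss. Pooled-variance formula, with p̄ = 0.25:

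n = [1.96·√(2p̄(1−p̄)) + 0.8416·√(p0(1−p0) + p1(1−p1))]² / (p1−p0)²

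= [1.96·√0.375 + 0.8416·√0.355]² / 0.04 = 72.4 per arm.

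Inflated for loss: 72.4/0.9 = 80.4, so 81 per arm and 162 in total, as stated. With 81 × 0.9 = 72.9 evaluable per arm, power is 80.3%. The arithmetic is sound; only the premise is in question.

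**2. Set up the mixed cohort.** Let f be the share at or below 130/80 at baseline, s the share of these who are controlled at six months under usual care, and e the intervention effect among them. Then

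p0 = f·s + (1−f)·0.15 and p1 = f·(s+e) + (1−f)·0.35.

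The documents give none of f, s or e. All three are assumptions, as is applying 15% and 35% unchanged to the participants uncontrolled at baseline.

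**3. Results at 73 evaluable per arm (162 enrolled).**

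| f | s | Rates, e = 0 | Power, e = 0 | Rates, e = 20 points | Power, e = 20 points |
|---|---|---|---|---|---|
| 10% | 50% | 18.5% vs 36.5% | 69% | 18.5% vs 38.5% | 77% |
| 10% | 70% | 20.5% vs 38.5% | 67% | 20.5% vs 40.5% | 75% |
| 20% | 50% | 22.0% vs 38.0% | 56% | 22.0% vs 42.0% | 74% |
| 20% | 70% | 26.0% vs 42.0% | 53% | 26.0% vs 46.0% | 72% |

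**4. The same at the enrolment target.** 652 enrolled gives 326 × 0.9 = 293 evaluable per arm. Power is above 99.9% at f = 0, and 98.5% in the worst row of the table (f = 20%, s = 70%, e = 0).

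**5. Is f of 10-20% plausible?** As a rough guide, simulate repeated BP readings as bivariate normal. Section I (A7) gives a treatment-group mean of 136.2/82.8 before intervention in the team's earlier comorbid cohort. Assumed: SDs of 15-18 systolic and 9-10 diastolic, between-visit correlation 0.5-0.7, systolic-diastolic correlation 0.5-0.6, and qualification when either component is high. Among people qualifying on one reading, about 12-17% are at or below 130/80 on a second.

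**6. What that simulation implies for the control arm.** Treat the six-month reading as a third exchangeable reading, with no trend or treatment change. Of those controlled at baseline, 32-39% are controlled again; of the rest, 8-13% become controlled. Overall, 12-17% are controlled at six months, which brackets the plan's 15%. So the simulation supports some participants being controlled at baseline, but supports neither the 50-70% persistence used in step 3 nor a control-arm rate above 15%.

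**The case against.** The best defence has four parts.

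- **The 15% may already allow for this.** B2 reports almost no change in past control groups and then allows 15% as a conservative figure. A reader might infer that the loose entry rule pushes the control-arm rate above 15%. The documents do not show that, and step 6 gives 12-17% overall. This part stands. It does not rescue the sentence in B2, which ties the rates to an all-uncontrolled cohort.
- **The power loss depends on chosen inputs.** A reader might take 53-69% as the trial's true power. It is not. It needs persistence of 50-70%, which has no source in the documents, 15% control among the remainder, and no effect in those already controlled. Letting the 20 points apply there raises it to 72-77%. This stands, so the figures are illustrations of sensitivity only.
- **The enrolment target is 652.** At that size power stays above 98% in every row. This stands. But B2 justifies only 162, and the documents do not reconcile the two numbers, which is a separate matter. Extra participants also do not change what the endpoint means.
- **Randomisation protects the comparison, and status at six months is a legitimate outcome.** Both true. Baseline-controlled people are expected equally in both arms, so a reader who infers a biased treatment effect would be wrong. The 140/90 analysis is also only an alternative measure, and a looser threshold is met by more people by construction. What remains is interpretation and precision.

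**Conclusion.** The contradiction between VII.B2 and criterion (f) in V.A is real, and nothing else in the documents resolves it. The exact claim is that some participants may already be controlled at baseline. That some certainly are is a likely inference, but the documents give no proportion.

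Four consequences hold: the premise behind the power statement is not guaranteed by the entry rule; the stated power of more than 80% at 162 is conditional on that premise; the endpoint combines becoming controlled with staying controlled, visibly so for 140/90; and the primary model leaves out a predictor that is already collected. On the assumptions in step 3, power at 162 falls to about 53-69%, or 72-77% with the full effect in the controlled subgroup. At 652 the loss is immaterial in these scenarios. There is no between-arm bias. The point is worth correcting because the remedy is cheap; it does not threaten the validity of the trial.

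**What to change.** 1. Reconcile V.A and VII.B2 by correcting the B2 sentence so that it describes the population criterion (f) admits.
2. State power as conditional on the share controlled at baseline. Show a range such as 10-20%, with the assumed persistence and the assumed effect in that subgroup written out.
3. Add baseline SBP and DBP from the baseline survey as covariates in the primary logistic model (equation 1).
4. Prespecify two supportive analyses: the 130/80 result in participants above 130/80 at baseline, and the 140/90 result in those at or above 140/90 at baseline. Report each beside the result in all participants.

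The cost is SAP wording and a less favourable stated power. No new data are needed, since BP is already measured at the baseline survey.
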